##### **Coronary Artery Ostia Obstruction and Intervention**

The secondary effectiveness analysis will present the following:

Frequency distribution and the corresponding 95% confidence interval of patients with:

- Coronary artery ostia obstruction related to the intervened leaflet within 30 days post-procedure, as determined by the CEC
- Coronary artery intervention related to the intervened leaflet within 30 days post-procedure, as determined by the CEC

For patients who experienced any of the above events, a by-patient listing will be provided with extended event description, time from the procedure and relation to ShortCut device and/or ShortCut procedure.

#### **10.4.9 Per Protocol primary effectiveness analysis**

For the Per Protocol primary effectiveness analysis, the primary effectiveness analysis will be repeated using the PPPE analysis set.

#### **10.4.10 Per Protocol secondary effectiveness analysis**

For the Per Protocol secondary effectiveness analysis, the secondary effectiveness analysis will be repeated using the PPSE analysis set.

#### **10.4.11 Technical success analysis**

The technical success analysis will be performed on the safety analysis set.

Frequency distribution of patients with technical success will be presented along with a 95% confidence interval, including the rate of each individual component.

For patients that did not have technical success, a by-patient listing will be provided with detailed description of the reason.

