### 6.2.3 Technical success endpoint

A composite of the following, which will be assessed at exit from procedure room following the ShortCut™ procedure:

- Successful access, delivery, and retrieval of the ShortCut™ device
- Freedom from ShortCut™ device- and/or ShortCut™ procedure-related mortality
- Freedom from ShortCut™ device- and/or ShortCut™ procedure-related:
  - Surgery or intervention
  - Major vascular or access-related complications
  - Cardiac structural complication

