## 8.2 Main Exclusion criteria

1. An excessive aortic valve leaflet Calcium morphology, such as diffuse massive calcification at the targeted leaflet for splitting or anatomy not suitable for the use of the ShortCut™device, as determined by the CT measurements.
2. Leaflet planned to be intervened is torn pre-ShortCut device access.
3. Patient has iliofemoral vessel characteristics that preclude safe insertion of the introducer sheath.
4. Planned concurrent intervention in the same setting of the index procedure.
5. Surgery or interventional procedure ≤ 1 month prior to the index procedure.
6. Planned provisional (pre-position coronary artery) stents.
7. Coronary disease that, in the opinion of the local Heart Team, should be treated; or treatment of coronary disease ≤ 1 month prior to index procedure.
8. Carotid or vertebral artery disease that, in the opinion of the local Heart Team, should be treated; or treatment of carotid stenosis ≤ 1 month prior to index procedure.
9. CVA or TIA ≤ 6 months prior to index procedure.
10. Severe neurological disability, as determined by the Investigator.

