## 10 Statistical Analysis Plan

### 10.1 Study Analysis Sets

#### 10.1.1 Safety analysis set

The safety analysis set will include all patients who reached the point of index procedure, i.e., patients in whom the ShortCut device was introduced through the introducer sheath. Patients who were treated with the ShortCut without meeting the eligibility criteria will also be included in this analysis set.

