### 10.2 Sample Size Considerations

The data gathered in this continued access phase will support the objectives and outcomes of the original IDE pivotal study. Therefore, the study endpoints will not be statistically powered. The analysis for the efficacy and safety of the Shortcut™ device will follow a designated statistical analysis plan. Continued Access studies are approved by FDA on a time-limited phased basis, therefore sample size in this study will be based upon FDA-approved limits. The first enrollment study phase will include up to 30 enrolled patients:

- Up to 24 patients for whom the ShortCut™ procedure was initiated and either the following occurred:

- Split was attempted and were determined to have adequate Imaging
- Split was not attempted for any reason, or
- Split was attempted but were determined to have Inadequate Imaging
- Up to 6 additional enrolled patients who dropped out from the study prior to the index procedure (before the ShortCut™ procedure was initiated), due to: death, consent withdrawal by patient or by physician, patient lost to follow up, or other reasons).

Following this phase and subject to FDA's approval, expansion of the study for the inclusion of up to 20 additional enrolled patients according to time-limited phased basis agreed with the FDA.

The population flowchart is provided below:

[figure not shown]

Figure 1: Study population flowchart

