### **10.4.2 Patient disposition**

Patient disposition will be tabulated; the number of enrolled, treated, prematurely terminated and completed patients will be summarized. Baseline demographics and characteristics will be summarized at the level of patient.

A list of dropouts will be prepared including reason for discontinuation and time of discontinuation.

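### Technical success includes successful access, but its denominator admits only patients in whom the device was already introduced, so a failed access or introduction is left out and not counted as a failure

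*Combined protocol and SAP*

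**What the plan says.** Section 6.2.3 defines technical success as a composite assessed when the patient leaves the procedure room after the ShortCut procedure. Its first component is "Successful access, delivery, and retrieval of the ShortCut™ device". The others are freedom from device- or procedure-related death, from related surgery or intervention, from related major vascular or access complications, and from related structural cardiac complications.

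Section 10.4.11 sets the population: "The technical success analysis will be performed on the safety analysis set". It adds that the number of patients with technical success "will be presented along with a 95% confidence interval, including the rate of each individual component", and that patients without technical success will be listed individually with the reason.

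Section 10.1.1 defines the safety set as those who reached the index procedure, meaning "patients in whom the ShortCut device was introduced through the introducer sheath".

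Section 10.2 allows up to 30 enrolled patients in the first phase. Up to 24 have the ShortCut procedure initiated, and up to 6 are "additional enrolled patients who dropped out from the study prior to the index procedure". Section 10.4.2 adds: "A list of dropouts will be prepared including reason for discontinuation and time of discontinuation".

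**The concern.** The endpoint asks, among other things, whether access was achieved. The analysis set admits a patient only once the device has gone in through the sheath. Entry to the denominator is thus conditional on part of the outcome being measured.

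Two kinds of patient are affected. One is a patient in whom access or introduction was attempted and did not succeed. The other is a patient with a procedure-related vascular or access complication that prevented introduction. Both would fail the composite, and neither can enter it. No other analysis set picks them up: the effectiveness sets in 10.1.2 and 10.1.3 require an attempted split, and the per-protocol sets in 10.1.4 are subsets of those.

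What is at stake is the meaning of a reported rate. Sections 5 and 10.2 say the data will support the pivotal study. A reader who sees a technical success rate, with a separate rate for the component that contains access, will take it as a rate among patients in whom the procedure was tried.

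**Working it through.** **1. Who can be in the denominator**

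| Situation | In safety set (10.1.1)? | Effect on the rate in 10.4.11 |
|---|---|---|
| Lost before any access attempt (death, withdrawal and so on) | No | None, properly excluded |
| Access or introduction attempted, device not introduced | No | None, although component 1 of 6.2.3 is not met |
| Access complication that prevented introduction | No | None, although 6.2.3 is not met |
| Device introduced, delivery or retrieval fails | Yes | Counted as failure |
| Device introduced, related complication later | Yes | Counted as failure |

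The gap is confined to the second and third rows.

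**2. What access means.** No definition appears in the text provided. Section 10.1.3 lists access as a ShortCut procedure step ahead of delivery to the valve. The second exclusion criterion in section 8.2 ("Leaflet planned to be intervened is torn pre-ShortCut device access") speaks of access by the device. If access means vascular access or introduction, that part cannot fail within the set. If it extends beyond the sheath, that further part can still fail within the set. On either reading, a patient whose device was never introduced is absent.

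**3. Where 10.2 would place such a patient.** The plan's own enrolment figure reproduces: 24 + 6 = 30. Which group a failed-access patient joins is not explicit, because initiation of the procedure is not defined directly. Section 10.2 appears to equate it with the index procedure, which 10.1.1 ties to introduction; that would put the patient among the 6. Section 10.1.3 treats access as a procedure step, which could put the patient among the 24. The patient is outside the safety set in both cases.

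**4. Size, as an illustration**

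Inputs: 24 patients in the safety set (the upper limit in 10.2), all successful (assumed), and k omitted failures (assumed, because the documents give no count). Section 10.4.11 names no interval method, so Clopper-Pearson is also an assumption. Sections 10.4.7 and 10.4.8 name it for splitting success.

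Rate = 24 / (24 + k). For x successes in n, the lower limit is the 0.025 quantile of Beta(x, n − x + 1) and the upper limit is the 0.975 quantile of Beta(x + 1, n − x). When x = n, the lower limit is 0.025^(1/n) and the upper limit is 1; for n = 24, 0.025^(1/24) = 0.858.

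| k | Successes / patients | Rate | 95% interval |
|---|---|---|---|
| 0 (as planned) | 24/24 | 100% | 85.8 to 100 |
| 1 | 24/25 | 96.0% | 79.6 to 99.9 |
| 2 | 24/26 | 92.3% | 74.9 to 99.1 |

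If the failed patient is instead one of the 24 initiated, the plan reports 23/23 = 100% where an attempted-access rate would be 23/24 = 95.8%. The loss per omitted patient is about the same.

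**5. Direction.** Each omitted patient adds one to the denominator and nothing to the numerator. The safety-set rate can therefore equal or exceed the attempted-access rate, but never fall below it.

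**The case against.** The strongest reply is that a rate among patients in whom the device was introduced is a legitimate measure of device performance, and that the plan states this population openly. If the pivotal study used the same denominator, which cannot be seen here, changing it could harm comparability. This has force as a reason to keep the safety-set rate available. It does not make that rate a measure of an endpoint that names access as a component.

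The document is also a synopsis. It refers to a designated analysis plan, and its population flowchart is not shown, so definitions may exist elsewhere. That is a reason to word the point as holding for the text provided. The set and the endpoint are both stated here, however, and they do not fit together.

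The third exclusion criterion screens out vessels unsuitable for sheath insertion, so failed access may be rare or absent. That stands. The dropout list in 10.4.2 may also show such patients, but a listing does not enter the rate or its interval.

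Two stronger readings are tempting, and the documents support neither:

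- A reader might infer that the access component is 100% by construction. That holds only for the part up to introduction, because access is undefined.
- A reader might infer that all 6 pre-procedure dropouts could be hidden access failures, giving 24/30 = 80.0%. Section 10.2 names death, withdrawal and loss to follow-up as reasons, leaves other reasons open, and does not mention failed access. There is no basis for that scenario, or for calling any particular count more plausible.

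**Conclusion.** The point holds in a limited form and is a cheap improvement. As written, 10.4.11 cannot count a failed ShortCut access or introduction as a technical failure, nor an access complication that prevented introduction. Delivery and retrieval failures, and complications after introduction, are counted correctly.

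The direction is certain whenever such a patient occurs; the size is not known. With a full safety set of 24, all successful, each of the first two omitted failures would cost about 4 percentage points (100% to 96.0% to 92.3%). With no such patients there is no effect. These figures illustrate sensitivity to the denominator and do not measure a bias. The endpoints are not powered and results are descriptive, so what changes is how the rate may be read, not any decision rule.

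**What to change.** In 10.4.11:

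- Analyse technical success in all enrolled patients in whom access for the ShortCut procedure was attempted.
- Define access, and state the step at which an attempt begins, kept distinct from access for the planned TAVR.
- Count failed access or failed introduction as technical failure, assessed at exit from the procedure room, and include these patients in the by-patient listing with the reason.
- Show the rate on the safety set as a supportive row, so the currently planned figure stays available for comparison with the pivotal study.
- Name the confidence interval method.

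Leave the safety set in place for the safety analyses, and leave the enrolment limits unchanged.

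The cost is some wording, one extra denominator, and a record at the procedure of whether access was attempted, since a dropout reason alone may not supply it. The rate may look slightly less favourable.

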#### **10.4.12 Covariate analysis**

Covariate analysis will examine descriptively whether the study results are affected by different patient characteristics. Due to the relatively small sample size, the number of covariates will be limited to age, sex, race and ethnicity.
